- xi. Exercise Testing: Whole body steady state submaximal O₂ consumption will be determined during a standard 6 min treadmill test (2.5mph) to determine VO₂ cost. Participants will then complete a ramped treadmill test (Bruce protocol) to determine cardiorespiratory fitness (VO₂ peak) and peak heart rate as previously described (13). We will also investigate post exercise oxygen consumption and heart rate at 60, 90, 120, and 300 seconds after cessation of the max test to determine if exercise recovery is impacted by statins. Blood will be sampled for measurement of CK 20-30 minutes following the maximal exercise to assess potential muscle damage. Exercise testing will be repeated at 1, 6, and 12 months.
- xii. Cardiovascular Function: These measures include both heart rate and stroke volume performed under both resting and sub-maximal exercise conditions (performed on separate days) (80). Stroke volume will be estimated by finometer placed on finger (80). Cardiovascular function will be repeated at 6 and 12 months.
- xiii. Physical Activity Monitoring: Physical activity levels and sedentary time will be assessed by pedometers and accelerometers for 5 day periods. Physical activity monitoring will be repeated at 1, 6 and 12 months.
- xiv. Statin Therapy Intervention: Once participants have successful completed baseline testing, the participant will be randomly assigned to 1 of 3 groups (1:1:1 ratio). Statins will be prescribed as a placebo or at a dosage of 20 or 80 mg/day (atorvastatin; Lipitor) by the study physician at KUMC, [name], MD. Participants and research team will be blinded to the type and dose of statin. Statins will be dispensed by KUMC investigational pharmacy at regular intervals during the participant's enrollment in the study. The study physician will provide care for any problems associated with the statin treatment after unblinding by Data Safety Monitoring Board, [name]. All doses fall within the norms of recent recommendations and are given chronically (2).

F. Risk/benefit assessment:

a. Potential risks:

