 - c. Providing on-going information to the study sponsor and the IRB: PI, Study Coordinator
 - d. Maintaining participant's research records: PI, Study Coordinator
 - e. Completing physical examination: PI, CTSU Nurse
 - f. Taking vital signs, height, weight: CTSU Nurses
 - g. Drawing / collecting laboratory specimens: CTSU Nurses
 - Performing / conducting tests, procedures, interventions, questionnaires: PI,
 Study Coordinator
 - i. Completing study data forms: Study Coordinator
 - j. Managing study database: PI

K. Assessment of Subject Safety and Development of a Data and Safety Monitoring Plan

- **a. Key personnel:** [name], [name], [name], [name], study physician at KUMC and [name], study physician at ECU.
- b. Plan for safety monitoring and review: [name] will serve as the Chair of the Data Safety Monitoring Board and will convene every 6 months with the other members, Drs. [name] and [name] to make decisions on safety of the participants. Enrollment data will also be reviewed twice a year by the DSMB. In addition, data will be reviewed on a yearly basis with the biostatistician, [name] to determine if the studies should be shortened do to either no measured effect or due to effects that are greater than what power calculations indicated. If problems occur with participants, blinded study staff will alert [name]. [name] will have access to dose and type of statin and will consult the study physicians/cardiologist to make a decision on whether the subject should be removed from the study for safety concerns. The PI and other key personnel will be examining research data on a subject to subject basis to ensure it is accurate and to address any potential problems that may arise with the protocols. In addition, Drs. [name] and [name] will discuss data at least once per month through in person meetings or by phone to ensure that data collection is occurring in a consistent manner at both locations.
- **c. Plan for adverse event reporting:** Adverse events will be defined as any untoward medical occurrence in study participants or others immediately involved in the

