performance of the protocol, which does not necessarily have a causal relationship with the study treatment, but results in a change in intervention, daily function, hospitalization or rated category 3 or above using the National Cancer Institute Common Terminology Criteria for Adverse Events (CTCAE) v3.0. Expected events such as slight muscle soreness consistent with statin therapy, or those consistent with a participant's prior medical history not sufficient to alter the intervention will not be considered an AE. Staff involved in performance of the protocol (e.g. coordinators) will continually monitor participants for adverse events throughout the intervention, and study staff will assess adverse events at every testing visit as well as during regularly scheduled telephone assessments with all randomized participants.

If study staff, tester, or participant reports adverse events or complaints, relevant information will be collected and documented. The participant will be evaluated by the unblinded investigator identified in the protocol. The investigator will determine the severity (according to the CTCAE) and relatedness of the AE to the intervention. The investigator will identify adverse events of clinical concern, those that may require further workup, or suggest that additional participation in the intervention might be a safety risk. These AEs will first be discussed with the participant and then communicated to the study staff or providers with participant's consent and as appropriate. Serious adverse events directly related to the intervention will be reported immediately to the IRB. Any adverse event rate over 30% in 12 months will be reported to the NIH.

III. Subject Participation

A. Recruitment:

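### Adverse-event severity and relatedness are set by an unblinded investigator, and this double-blind trial plans no blinded rating

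*Combined protocol and SAP*

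**What the plan says.** Section II.B calls the design double-blinded, and II.E.a.xiv states: "Participants and research team will be blinded to the type and dose of statin". The same item has the study physician caring for statin-related problems "after unblinding by Data Safety Monitoring Board".

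Section II.K.c sets out what happens once staff, a tester or the participant reports an adverse event or complaint. Information is first collected and documented. Then: "The participant will be evaluated by the unblinded investigator identified in the protocol". The next sentence reads: "The investigator will determine the severity (according to the CTCAE) and relatedness of the AE to the intervention".

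Section II.K.b covers removal. It begins "If problems occur with participants, blinded study staff will alert" and goes on to a person, whose name is removed from the public text, who "will have access to dose and type of statin" and confers with the study physicians or cardiologist in order to "make a decision on whether the subject should be removed from the study for safety concerns".

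Neither section, nor any other part of the protocol, provides for a blinded rating, blinded adjudication, or a rule that grading comes before the code is opened.

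**The concern.** Unblinded access for someone with a safety role is normal and is not the problem. The problem is that the recorded severity and relatedness ratings come from a person described as unblinded. Both are matters of judgement. The trial's stated hypothesis is dose- and duration-dependent harm to muscle, and muscle complaints are the events most likely to be reported, so an assessor who knows the arm has a ready expectation to apply.

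Three things in II.K.c depend on these judgements. A grade of 3 or above is one of the criteria that make an occurrence an adverse event. Serious events judged directly related to the intervention go to the IRB at once. Slight soreness in keeping with statin treatment is treated as expected and is not counted as an adverse event. A lesser concern is removal: if discretion is exercised with the code to hand, the participants who reach month 12 may differ between arms partly because of that.

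**Working it through.** The plan gives no figure on this point, so the check sets its provisions side by side.

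1. **Who rates.** II.E.a.xiv blinds the research team. II.K.c gives severity and relatedness to an unblinded investigator. Both can be true if that investigator is deliberately placed outside the blind, but the ratings on record are then arm-aware by design. This is a stated rule, not a missing detail.

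2. **What the rating controls.** Under the II.K.c definition, an occurrence counts as an adverse event if it leads to a change in the intervention, in daily function, to hospitalization, or to a grade of 3 or above. The grade can therefore decide whether the event is counted, and a decision to change treatment taken with knowledge of the arm can do the same. Relatedness governs the immediate IRB report of a serious event. The count feeds the report to the NIH when the rate passes 30% in 12 months.

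3. **Who decides what is expected.** II.K.c excludes slight soreness consistent with statin therapy but does not say who applies the exclusion. Complaints as well as events go to the unblinded investigator, so the decision may be made there. A person who knows the participant is on placebo cannot apply that wording in the same way as for a participant on 80 mg.

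4. **Direction.** Knowing that a participant is on 80 mg could raise the grade and the attribution. It could equally lead the same soreness to be set aside as expected. The text does not favour one over the other.

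5. **Removal.** The routes out of the study are not alike:
   - Under II.K.b, a person with access to the code consults the study physicians or cardiologist and a case-by-case decision follows. Arm can enter here.
   - Under II.D.b and II.F, participants with elevated CK or ALT are taken out. As worded, this does not turn on that person's opinion, although neither section gives a cut-off.
   - Under II.D.b, participants may leave at any time. This does not turn on that person's opinion either.

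6. **Link to the month-12 outcome.** II.C and V.A use a mixed model on the available data and describe no sensitivity analysis for dropout that differs by arm. To size an effect one would need the share of removals made by discretion, how far knowledge of the arm shifts that share, and how removal relates to later respiration. The documents give none of these.

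**The case against.** The case on the other side has real force on several points.

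- **The listed muscle outcomes are not affected.** Algometer thresholds, 0-10 pain ratings, the pain questionnaire and CK do not pass through the unblinded investigator. The objectives in II.A and the analysis in V.A specify no between-arm comparison of adverse events. This stands, and it confines the point to recorded safety ratings and the reporting that rests on them.
- **Removal is not one person's call.** Blinded staff raise the problem, physicians are consulted, and two other routes out exist. This stands. A reader might infer that dropout as a whole is driven by expectation. The documents do not support that. II.K.b also says only that the person has access to the code, not that it is opened in every case. With names removed, it cannot be confirmed that this person is the unblinded investigator of II.K.c.
- **Blinding would not equalise dropout.** If 80 mg truly causes more symptoms, removals would differ by arm under full blinding too. This stands. The remedy addresses only the part due to knowledge of the arm.
- **No sized bias follows.** A reader might take the roughly 15% with pain and weakness at 80 mg (II.F), suppose that all were removed and none on placebo, and assume a decline larger by 0.5 to 1 SD. That gives 0.15 × 0.5 = 0.075 SD to 0.15 × 1 = 0.15 SD, or 0.075/0.87 = 9% to 0.15/0.87 = 17% of the design effect size. The documents do not support this. The 15% is a symptom rate, not a removal rate, and the larger decline has no source. The sum describes a completers-only mean, whereas the mixed model also uses earlier visits. The 0.87 matches the NIRS pilot value (19.07/21.80 = 0.87). For the primary outcome the pilot value is 88.5/59.9 = 1.48, against which the same shifts are 5% to 10%.
- **No blinded physician is named.** This is true as far as it goes. However, II.E.a.xiv blinds the research team and has the study physician giving care once unblinding has occurred, which implies that this physician is blinded until then.

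None of this supplies a blinded rating.

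**Conclusion.** The point holds, within limits. As written, II.K.c produces severity and relatedness ratings made with knowledge of the arm in a trial described as double-blind, and no blinded rating is available to set beside them. Those ratings, and possibly the decision on what counts as expected, can be influenced by that knowledge in a direction that cannot be foretold.

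The secondary point is weaker: discretionary removals under II.K.b may depend partly on arm. The size of any effect on the month-12 outcome cannot be derived from the documents, and none is claimed. The conclusion rests on reading the two quoted sentences of II.K.c together, so that the investigator who rates is the unblinded one who evaluates the participant. It does not depend on whether that is also the code holder of II.K.b. The change is a cheap improvement.

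**What to change.** In II.K.b and II.K.c:

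- Have a team member who is still blinded record severity, relatedness and expectedness before the code is opened for that participant. This could be the study physician before any unblinding under II.E.a.xiv, or another blinded person designated from existing staff. Section IV.A unblinds the PIs and the biostatistician after one year, so the rater should not be one of them. If the code has already been opened to the rater for a participant, later events in that participant need a different blinded rater.
- Use these blinded ratings in safety reporting.
- Log each code opening with its date, reason and arm.
- Report removals by route (discretionary, enzyme-driven, voluntary) and by arm.

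Leave clinical decisions on removal and urgent unblinding unchanged. The cost is protocol wording, one extra recorded step, and a slight delay for non-urgent events.

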University of Kansas Medical Center RESEARCH PROTOCOL INVOLVING HUMAN SUBJECTS

Version date: 4/21/22

Principal Investigator: [name]

Study Title: Impact of statin therapy on muscle mitochondrial function and aerobic capacity

Co- Investigator(s): [name], [name], [name]

I. Purpose, Background and Rationale

A. Abstract

More than 40 million Americans are currently take statins for the treatment or prevention of hyperlipidemia and cardiovascular disease (CVD). Based on the new usage guidelines from the American College of Cardiology and the American Heart Association (ACC/AHA) (2), that number is expected to increase to over 60 million (3), reflecting the growing sentiment for more wide-spread use of statins, even in otherwise asymptomatic patients. Although generally well-tolerated, statin therapy is not without risks. The most common reported side effects include mild to moderate muscle weakness, fatigue and/or pain, the incidence of which increase as a function of both dose and duration of statin use (4, 5). Stating also increase the risk of developing more serious metabolic conditions, including insulin resistance and type 2 diabetes (6-9). The underlying mechanism(s) for these complications is unknown. In recent years however, evidence has been mounting from both cell culture and animal models that statins interfere with mitochondrial function in muscle (10-12). In the present application, we provide data from both ex vivo and in vivo preliminary studies in humans suggesting that statins induce progressive and quite striking reductions in skeletal muscle mitochondrial respiratory function. The overall aim of the study is to determine the impact of low and high dose statin therapy on skeletal muscle mitochondrial function, insulin sensitivity, and cardiorespiratory fitness. Our hypothesis is that statin therapy produces a decline in mitochondrial respiratory function in skeletal muscle that is both dose and duration dependent, compromising metabolic and cardiorespiratory function.

B. Background and Significance

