for 10% dropouts. The subject enrollment will be split equally between the two sites (15 participants/group per site). For this study, our primary analysis is to use mixed model to test the interaction between group and time, which is expected to be more powerful than the two-sample t-test because all repeated measurements will be considered in modeling, baseline patient characteristics can be controlled statistically, and participants with missing data can be included for analysis.

D. Subject Criteria

a. Inclusion criteria/Exclusion criteria:

- i. Inclusion Criteria
 - Ages 35–65 years
 - BMI between 25-43 kg•m²
 - >5% risk for a cardiovascular event in the next 10 years according to the 2013 American College of Cardiology/American Heart Association risk calculator and/or 2 out of 5 metabolic syndrome risk factors (Triglycerides ≥ 150 mg/dL; HDL ≤ 40 mg/dL; Glucose ≥ 100mg/dL; Waist Circumference ≥ 102cm for males, 88cm for females; Blood pressure: ≥ 130mmHg systolic and/or 85mmHg diastolic or being treated for hypertension) and/or LDL-Cholesterol >120 mg/dl.
 - Stable doses of medications for 90 days
 - Willing to stop all NSAIDs and aspirin for 7 days prior to muscle biopsy

[figure not shown]
ii. Exclusion Criteria

- Smoking
- Previous use of statins
- Use of other medications or supplements that affect lipid profiles or body weight in the last 6 months
 - o e.g., fibric acids, bile acid sequestrants, nicotinic acids, fish oil
- Diagnosis of chronic diseases including CVD, other metabolic diseases (e.g., thyroid), current diagnosis and active treatment of cancer, HIV, or acquired immunodeficiency syndrome.
- Diagnosis of type 1 or type 2 diabetes at the time of screening (fasting blood glucose >126mg/dL). If evidence of type 2 diabetes outcome measures is detected during the course of the study (fasting glucose > 126 mg/dl or HbA1c > 6.5%) we will notify the participant to contact their physician.
- History of abnormal bleeding problems
- Currently taking (within the last 10 days) anti-platelet medication (Plavix), Warfarin, and other anti-coagulants (eliquis, pradaxa, and xarelto) medications.
- >2 fold upper normal limit (UNL) for ALT or creatinine
- Women who are pregnant or breastfeeding
- Individuals with polymorphism (SLCO1B1) known to be associated with susceptibility for statin induced myopathies (tested at screening)
- Currently enrolled in another research study

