- ii. Statins: Statin therapy is associated with muscle issues that range from more minor issues of muscle pain, cramping and fatigue, to myopathies, to the very severe issues of rhabdomyalgia, although this is rare. Statins are the most prescribed drug in the world. Statins are also associated with headaches, nausea, and constipation. Statins are also not well tolerated by athletes suggesting that exercise may worsen the effects of statins on skeletal muscle. Thus, there is the potential that participants in our study may have adverse effects while taking statins. A recent trial conducted by our consultant, [name], utilized 80 mg/day of atorvastatin and found that ~15% of participants experienced pain and weakness (2). atorvastatin 80 mg is an increasingly common dose because three large clinical trials, REVERSAL (atorva 80 v. prava 40, n=502) (3), PROVE IT (atorva 80 v. prava 40, n=4,162) (4), and TNT (atorva 80 v. prava 10, n=10,001) (5) demonstrated reduced atherosclerosis and cardiac events with atorvastatin 80 mg. These studies were done in CAD patients, a group on multiple other medications and likely to be at higher risk for side effects than our healthy participants. Nevertheless, side effects were rare. Liver function test (>3 times upper normal limits [UNL]) and creatinine kinase (CK) elevations (> 10 UNL) occurred in only 1-3.3% of patients treated with atorvastatin 80 mg for up to 24 months, respectively. These side effects should be even more rare given that we will pre-screen and exclude individuals with polymorphisms (GATM and SLC01B1) that increase risk for myopathy. We will test both muscle enzymes (creatine kinase) and liver enzymes (ALT) to determine if statins are causing either muscle myopathies or liver injury. This testing will occur at baseline and at 1 month into taking statins. If enzymes are elevated, the subject will be taken out of the study for their own health. Finally, study physicians at both KUMC who commonly prescribe statins and deal with patients who experience statin induced problems will provide medical coverage for our studies. Participants are free to abstain from taking their statins and leave the study at any time. Importantly, most individuals report that statin induced complications go away very quickly after stopping the therapy. Participants who are discontinued from the study for a medical reason judged to be appropriate by the study doctors will receive the same reimbursement as if they completed the study to avoid the possibility that a subject would "soldier on" simply for the reimbursement.

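### The adverse-event definition leaves out mild muscle symptoms and gives laboratory-detected diabetes no stated route in, so event counts can understate both harms the plan names

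*Combined protocol and SAP*

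**What the plan says.** - **Threshold (II.K.c).** An AE need not be causally related to study treatment, but it must be one that "results in a change in intervention, daily function, hospitalization or rated category 3 or above", graded by CTCAE v3.0.
- **Exclusion (II.K.c).** "Expected events such as slight muscle soreness consistent with statin therapy" are set aside, together with events in keeping with the participant's medical history. The sentence ends "not sufficient to alter the intervention will not be considered an AE".
- **Handling (II.K.c).** "If study staff, tester, or participant reports adverse events or complaints, relevant information will be collected and documented". An unblinded investigator then judges severity and relatedness. Staff ask about AEs at every testing visit and in scheduled telephone calls. An AE rate above 30% in 12 months is reported to the NIH.
- **Harms named (I.A).** "The most common reported side effects include mild to moderate muscle weakness, fatigue and/or pain", with incidence rising with dose and duration. Insulin resistance and type 2 diabetes are named as more serious risks.
- **Diabetes found on study (II.D.a.ii).** The criterion and the only stated action are: "fasting glucose > 126 mg/dl or HbA1c > 6.5%) we will notify the participant to contact their physician".
- **Analysis (V.A).** A mixed model by group and time is applied to respiration and the other outcome variables. No analysis of AEs is described.

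**The concern.** The trial asks whether a statin harms muscle and metabolism according to dose and duration. The milder muscle symptoms are where the plan itself expects a dose-related signal, yet they fall outside its event record.

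The exclusion also rests on a causal test, namely whether the soreness fits statin use. That sits badly in a definition that otherwise does not require causality, within a process where relatedness is judged by someone who knows the allocation. If that person also applied the exclusion, the same soreness could be treated differently by arm. The plan does not say who applies it.

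For diabetes the difficulty is silence. A participant can meet the criterion, be told to see a physician, and never appear as an event. What is at stake is the AE count by arm, the 30% trigger, and whatever part of the safety board's review relies on AE counts. The primary analysis of mitochondrial respiration is not affected.

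**Working it through.** The plan gives no figure here to reproduce. The check is mainly a reading of the sections side by side.

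**1. Muscle symptoms against the definition**
- Symptoms below category 3 that change neither treatment nor daily function, and do not lead to hospitalization, fail the threshold even without the exclusion. This covers mild symptoms, and moderate ones where they meet those conditions.
- The exclusion then bites on slight soreness that did affect daily function. It may also reach soreness that altered treatment, depending on whether the closing qualifier applies to the soreness clause or only to medical history. On either reading, slight soreness that does not alter treatment is out.
- Deleting the exclusion alone would therefore recover little. The threshold does most of the filtering.

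**2. What is captured elsewhere (II.A.b, II.E.a)**
- Pain: questionnaire, 0-10 ratings and algometer at months 1, 6 and 12.
- Strength and physical performance: months 1, 6 and 12.
- Creatine kinase: months 1, 6 and 12, and after exercise tests.
- Fasting glucose: months 1, 6 and 12; IVGTT at 6 and 12.
- No stated instrument: fatigue, cramp, and the start and stop dates of episodes between visits.

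**3. Diabetes against the definition**
- No sentence excludes diabetes. A laboratory finding that meets none of the threshold conditions falls outside by inference.
- HbA1c is part of the criterion in II.D.a.ii but appears in none of the blood panels in II.A.b.iv, II.E.a.ii or II.E.a.iv.

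**4. Illustration of size**
- Inputs: about 15% with pain and weakness on 80 mg in a cited trial (II.F.a.ii); at most 60 randomized 1:1:1 (II.B, II.C), so 60 / 3 = 20 per arm.
- Expected high-dose participants affected: 20 × 0.15 = 3. With the other group sizes in the plan, 15 × 0.15 = 2.25 and 30 × 0.15 = 4.5.
- The share mild enough to go uncounted is not given, so the range is 0 to 3 of 3.

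**5. The 30% trigger**
- The plan does not define the rate. Assume participants with at least one AE, pooled over arms: 0.30 × 60 = 18, so at least 19 of 60 are needed.
- With X binomial (60, p), P(X ≥ 19) is 0.0009 at p = 0.15, 0.149 at p = 0.25 and 0.437 at p = 0.30.
- Three high-dose participants add 3 / 60 = 5 percentage points to the pooled rate, so restoring them alone would seldom trip the trigger.
- If the true rate were 30% and the definition removed half of those participants (an assumption), the chance would fall from 0.437 to 0.0009. The trigger is sensitive to the definition only when the true rate is near 30%.

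**The case against.** The strongest reply is that little information is lost. Complaints are documented whether or not they are AEs. Pain, strength, creatine kinase and glucose are measured in every arm, and V.A allows each outcome to be compared by group and time. The pain ratings ask about usual as well as current pain, so they reach beyond the visit day. Raised enzymes lead to removal from the study (II.D.b, II.F.a.ii), arguably a change in intervention and so an AE. The safety board has a general remit, and staff are to alert its chair when problems occur (II.K.b). All of this stands.

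It also rules out several stronger readings that a reader might infer:
- *That neither harm enters the AE data.* Muscle events above the threshold count, and so would diabetes that met any of its conditions.
- *That complaints are heard and then discarded.* II.K.c says they are collected and documented.
- *That blinded staff apply the causal filter.* Relatedness is given to an unblinded investigator, and who applies the soreness exclusion is not stated.
- *That the HbA1c criterion can never be met.* It is unscheduled, but II.E.a.ii lets the study physician request extra tests.
- *That the safety board sees only events meeting this definition.* The plan does not limit it so, nor does it describe a final safety table.

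The reply does not close the gap. Scheduled outcomes are not event records, fatigue and cramp have no stated instrument, documented complaints need not be classified or tabulated by arm, and II.K.b does not say what the board receives.

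**Conclusion.** The point holds as one of event recording. The definition leaves out mild and some moderate muscle symptoms by an explicit rule, and laboratory-detected diabetes by inference from the threshold and a notify-only action. With no tabulation by arm of either as an event, AE counts and the 30% trigger can understate the two harms named in the Abstract.

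The documents do not allow the loss to be sized. About 3 high-dose participants with pain and weakness rests on the cited 15% applying here and on 20 per arm. How many would be judged slight is unknown, and no rate is given for new diabetes. It would be wrong to infer that a dose-related excess would go unseen, because the scheduled measures could still show it. The change is worth making because it is cheap and the trial is about these harms.

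**What to change.** In II.K.c:
- For safety recording, remove the exclusion of soreness in keeping with statin use.
- Record every new or worsened muscle symptom (pain, weakness, fatigue, cramp) of any grade, with start and stop dates and no causal filter, at the existing visits and calls.
- Log every case that meets the on-study diabetes criterion in II.D.a.ii.
- Give both to the safety board by arm at its 6-monthly review.
- Keep the present narrower definition for expedited reporting only, and say so.

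Separately, reconcile the HbA1c part of the criterion in II.D.a.ii with the blood panels in II.A.b.iv, II.E.a.ii and II.E.a.iv, which do not list it.

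The cost is extra lines on the event record and a table by arm for the board. No visits are added, since contacts, complaint documentation and fasting glucose are already in place. The drawback is a higher raw event count, including minor soreness after biopsies and exercise tests in all arms.
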